4.4. Selection of Clinical Sites/Labs

Not applicable. This is a single site study

5. Known and Potential Risks and Benefits to Participants

5.1. Risks of Investigational Product or Intervention as cited in Investigator Brochure or Package Insert

Daily food OIT dosing may cause normal allergic reactions, including anaphylaxis. Participants will be prescribed EpiPens® and trained in their use and they will have emergency plans in place with instructions to go to an emergency department in the event of an acute allergic reaction. The likelihood of a subject experiencing allergic symptoms will be lessened by the OIT protocol, starting at extremely small amounts of the shrimp protein for dosing under close medical supervision in the Stanford Food Allergy clinical research unit. Escalations are aborted at the first sign of an allergic reaction with equipment and medications (i.v. fluids, steroid, antihistamine, epinephrine) immediately available to treat allergic reactions. In the previous OIT studies milder reactions like oral pruritus or abdominal pain have successfully been managed by decreasing the rate of increase of OIT dosing and the use of antihistamines.

Ingesting an offending food allergen on a regular basis may worsen food allergy and result in allergic reactions to the offending food allergy such as hives, stomach pain, vomiting, diarrhea, runny nose or cough. It may also worsen skin allergy (eczema) or cause decreased weight gain, which will be monitored. Ingesting shrimp may also delay or prevent outgrowing the offending food allergy. The long-term effects of daily offending food allergen ingestion on growth have not been reported.

Complications of Oral Immunotherapy

During the initial desensitization period subjects may experience generally mild allergic reactions to the multi-food OIT. Although rare, the risk of severe anaphylaxis to OIT exists. In a recent review of over 352 subject undergoing OIT to peanut, Wasserman et al (9) reported that 95 subjects required the use of epinephrine at some point in the treatment. However, all cases resolved with the use of epinephrine and none escalated and needed further treatment suggesting that severe reactions during OIT are recognized promptly and treated appropriately.

5.2 Risks of Investigational Product or Intervention cited in Medical Literature

During the initial desensitization period subjects may experience generally mild allergic reactions to the multi-food OIT. Although rare, the risk of severe anaphylaxis to OIT exists. In a recent review of over 352 subjects undergoing OIT to peanut, Wasserman et al (9) reported that 95 subjects required the use of epinephrine at some point in the treatment. However, all cases resolved with the use of epinephrine and none escalated and needed further treatment suggesting that severe reactions during OIT are recognized promptly and treated appropriately.

In patients with food allergy, there have been many oral immunotherapy trials performed using procedures and dosing similar to those proposed in this Phase 2 trial. In general, safety profile has been very good across the studies, and based on those studies approximately 80%, 15% and <1% of the subjects are expected to have a mild, moderate, or severe symptoms, respectively, during some point in their dosing with the oral immunotherapy. It is important to note that essentially all adverse events have been allergy-related, predictable, and reversible. The only major atypical adverse event has been several reported cases of eosinophilic esophagitis, reversible upon cessation of dosing. There was a recent report of a fatal reaction to rush OIT to milk in a facility in Japan (Gordon Research Conference, Ventura, CA2018). Specifically, the buildup and daily maintenance doses of food OIT may cause allergic symptoms including sneezing, rhinorrhea, urticaria, angioedema, flushing, flares of eczema, ocular, nasal, oral and/or throat pruritus, nausea, vomiting, abdominal discomfort, cough, wheezing and/or shortness of breath in addition to severe anaphylaxis. Although no subject will be allowed to enroll who carries the diagnosis of eosinophilic disorder, the risk of eosinophilic esophagitis during OIT will be evaluated during the study. The likelihood of a subject experiencing any allergic symptoms is expected to be lessened by initiating dosing at extremely small amounts of characterized food allergen and by buildup dosing under observation in a clinical setting until the maintenance dose is achieved.

Oral food challenges may induce an allergic response. Allergic reactions can be severe including life-threatening allergic reactions; however, the risk of an allergic reaction is reduced by initiating the challenge with a very small amount of the food, gradually increasing the dose, and stopping the challenge at the first sign of a reaction. If subjects have an allergic reaction during the challenges, they may need oral, intramuscular, or intravenous medications. Subjects could have an IV catheter placed per clinician advice before the OFCs if they have a history of anaphylaxis with hypotension requiring IV fluid resuscitation. IV catheters may be placed, at physician discretion for any visit, based on factors such as previous reactions, recent clinical history, and clinical status observed during the visit. Trained personnel, including a study physician, as well as medications and equipment, will be immediately available to treat any reaction. The anticipated rate of life-threatening anaphylactic reactions would be < 0.1%.

There may be a risk that during participation in the trial the subjects may decrease their vigilance against accidental food allergen (cashew, or shrimp) ingestion because they believe they are protected from it. This phenomenon has been reported in previous trials, and subjects in the trial will be warned that they should continue to practice their usual vigilance against accidental ingestion of these foods.

5.2. Risks of Other Protocol Specified Medications

Epinephrine injection – Common side effects of epinephrine when used properly include anxiety; apprehensiveness; restlessness; tremor; weakness; dizziness; sweating; palpitations; pallor; nausea and vomiting; headache; and/or respiratory difficulties. Heart problems and stroke, particularly in the elderly and people with health problems, have been seen. Rare cases of serious skin and soft tissue infections have been reported at the injection site following epinephrine injection in the thigh.

It is very important to use proper techniques when giving epinephrine to avoid injury to the person administering the epinephrine or to the person receiving the injection. In addition to the common side effects above, accidental injection into the finger, hand or foot may result in loss of blood flow to the area causing paleness; coldness; numbness; bruising; bleeding; redness or damage to the bones. Epinephrine should not be injected into the buttocks and has resulted in cases of gas gangrene.

5.3. Risks of Study Procedures

Food allergen dosing (Initial dose day; Updosing; Oral food challenges):

A potential serious risk associated with the administration of food allergen is the risk of anaphylaxis. Symptoms of anaphylaxis may include pruritus, urticaria, angioedema, wheezing, cough, dyspnea, emesis, diarrhea, and hypotension that may progress to hypotensive shock.

The potential discomforts with the Initial dose day procedure, up dosing procedure, and oral food challenges are similar to the exposure to the suspected food in the past. Symptoms are usually transient lasting less than 2 hours and include pruritus, urticaria, nausea, abdominal discomfort, emesis and/or diarrhea, rhinitis, and sneezing and/or wheezing. The major risks involved include respiratory distress and rarely anaphylactic shock. Medication, personnel, and equipment are immediately available in the SNPRU to treat allergic reactions. Subjects will be provided a prescription and training for an EpiPen® or EpiPen, Jr.® or equivalent to have with them at all times and to use in case of an allergic reaction.

Phlebotomy:

Risks associated with phlebotomy or insertion of an intravenous catheter include infection, syncope, and localized pain, stinging, bleeding, or contusions at the phlebotomy site where the needle is inserted into the vein.

Skin prick test:

The risk involved with skin testing includes discomfort from the needle prick, along with erythema, urticaria, pruritus, and swelling at the skin test site in positive responses. Rare side effects include severe allergic reactions.

Spirometry:

The risk of a lung function test is the discomfort of exhaling forcefully. This may be associated with mild shortness of breath, slight dizziness, temporary cough and/or chest discomfort. Most patients do not have any symptoms.

5.4. Potential Benefits

There are no certain benefits to participating in this study. The only direct benefit to the participants is, for those participants who develop desensitization as a result of OIT, an ability to decrease their reactions to the offending allergen. The likelihood of this is unknown.

6. Investigational Agents

6.1. Cashew Flour or Shrimp Powder for OIT

The cashew flour and shrimp powder for OIT and food challenges, as well as placebo (oat) for food challenges, will be manufactured and provided by the Sean N Parker Manufacturing Facility. See 'Chemistry, Manufacturing, and Controls – Food Allergen Powder for Oral Immunotherapy' cross-referenced under IND# [REDACTED] for additional information.

6.1.1. Formulation, Packaging, and Labeling

The active study products, cashew and shrimp protein (provided as separate products), are characterized cashew and shrimp allergen in the form of cashew flour or shrimp powder, respectively, with no added excipients. The placebo used for the purpose of scheduled DBPCFCs is oat flour with no cashew or shrimp protein and no other added excipients. Please see 'Chemistry, Manufacturing, and Controls – Food Allergen Powder for Oral Immunotherapy' cross-referenced under IND# [REDACTED] for full detail.

6.1.2. Dosage, Preparation, Administration

Cashew flour and shrimp powder (and placebo where appropriate during OFC) will be provided in unit dose cups and stored as per manufacturer's recommendations at 36°F to 46°F (2°C to 8°C) to maximize stability. Research staff will administer doses to the participant orally in a non-offending, age-appropriate food vehicle. Dosage will be done per the protocol.

The SNP Center Manufacturing Facility complies with relevant sections of the Food Drug and Cosmetic Act (21 U.S.C. 351) for early phase products appropriate for a university-based clinical research program. Specifically, drug candidates are produced in compliance with current Good Manufacturing Practices (cGMP) as defined in 21 CFR 210 and 211. In addition, the cGMP unit adheres to pertinent sections of the July 2008 Guidance for Industry cGMP for Phase 1 Investigational Drugs. This document is intended to assist innovators involved with the manufacture of investigational drugs in early stage clinical trials. In order to manage the documentation requirements, Standard Operating Procedures

(SOPs) and standards set forth in the aforementioned FDA Guidances and Regulations, the SNP Center Manufacturing Facility uses an electronic document control system and will be reviewed and supported from trained research and regulatory personnel.

6.2. Drug Accountability

Under Title 21 of the Code of Federal Regulations (21CFR §312.62) the investigator will maintain adequate records of the disposition of the investigational agent, including the date and quantity of the drug received, to whom the drug was dispensed (participant-by-participant accounting), and a detailed accounting of any drug accidentally or deliberately destroyed.

Records for receipt, storage, use, and disposition will be maintained by the study site. A drug-dispensing log will be kept current for each participant. This log will contain the identification of each participant and the date and quantity of drug dispensed.

All records regarding the disposition of the investigational product will be available for inspection.

Following study drug administration, the site personnel will dispose of unused or partially used vials. All drug material will be released and recorded by the personnel.

6.3. Assessment of Participant Compliance with Investigational Agent

Families will document daily dosing and any reaction from at-home dosing on diary logs. Monitoring of compliance will be performed by reviewing the participant's diary and monitoring and counting their returned study medication. Unused study medication will be brought back to the SNP-CRU with each visit and collected by study staff for reconciliation of remaining IP product. In case of unforeseen circumstances that make an in-person visit in clinic difficult, doses may need to be sent to the participant's home.

6.4. Toxicity Prevention and Management (CoFAR guidelines will be used at all times unless specified otherwise)

6.4.1 Reactions to OIT During Initial Dose Day

The investigator will determine if the 5 mg dose was tolerated and if the participant can be sent home on that dose based on Appendix 3.

6.4.2 Reactions to OIT During build-up or Maintenance Phase

To be able to be eligible for an updosing or maintenance dose visit, subjects cannot have active wheezing, spirometry demonstrating FEV1 < 80% predicted and/or Peak Expiratory Flow (PEF) < 80% predicted or a current flare of atopic dermatitis that contraindicates updosing in the clinical judgment of the study physician. As needed, subjects will be maintained on their current dose of study product until their flare of asthma or atopic dermatitis is resolved.

If a subject has an updosing in the SNP-CRU without symptoms, the action should be to continue per protocol with daily home dosing of the tolerated dose with the next updosing visit 2 weeks later.

If the subject only experiences *oral/pharyngeal pruritus* during the administration of the daily dose, then the same dose can be repeated the next day at home and continued throughout the interval unless other symptoms begin to develop.

For other *mild objective symptoms* (Appendix 3), the action should be either to repeat the dose the next day (day 2) at home or to have the subject return to the SNP-CRU the next day (day 2) for a repeat of the previous day's dose or the last tolerated dose (at the study physician's discretion). If the dose is tolerated, then the subject will continue on that dose and return at the normal interval. If the dose causes mild symptoms again, then the subject may return to the SNP-CRU the next day (day 3) and be given the last tolerated dose or a 1-2 step dose reduction. If tolerated, the subject will continue on this dose for the normal time interval. If mild symptoms recur, a 1-2 step reduction should be administered the next day (day 4). If tolerated, then that dose should be continued for 2 weeks. If not tolerated, consultation with the PI is indicated.

If *moderate symptoms* (Grade 2, Appendix 3) occur, the action should be to have the subject return to the SNP-CRU the next day (day 2) for dosing with the previous days dose or the last tolerated dose, at study physician discretion, under OIT in Shrimp or Cashew allergy (MOTIF protocol) Version 4.0 26MAY2022

observation. If the dose is tolerated, the subject will continue on that daily home dose for the normal time interval per protocol. If the subject does not tolerate this dose, the subject should receive the last tolerated dose or a 1-2 step dose reduction the next day (day 3) in the SNP-CRU or at home if the planned dose was previously tolerated. If this dose is tolerated, it will be continued as the daily home dose for the normal time interval, then escalation attempted in the SNP-CRU as noted below. If this dose is not tolerated, then the next dose will be a 1-2-step reduction in dosing, and the dose will be given at the SNP-CRU on the next day (day 4). If this next dose is not tolerated, then a discussion with the PI will ensue to make a decision about whether to continue the subject on active treatment in the study.

If *severe* symptoms (Grade 3, Appendix 3) occur the action should be to treat the subject, and at the study physician's discretion either 1) have them return to the SNP-CRU the next day (day 2) for dosing with a 2-step reduction in dose under observation or 2) discontinue them from the active treatment. If the subject tolerates the dose reduction, then they will remain on that dose for 2 weeks and then return to the SNP-CRU for the dose escalation. A discussion with the PI may ensue to make a decision about whether to continue the subject on active treatment in the study.

If a subject fails dose escalation after three consecutive (with 2-4 weeks between) attempts, he/she will be considered a maintenance failure and the last tolerated dose will be accepted as the maintenance dose.

For a completed dose escalation with no symptoms, participants should be observed for 30 minutes. For mild symptoms, participants should have a one to two-hour post-protocol observation period. For moderate to severe symptoms, the observation period should be at least four hours and up to 24 hours based on symptoms and treatment regimen needed to stabilize the participant. Any subject deemed to have severe allergic reactions to OIT, including hypoxia, hypotension or change in mental status and receives aggressive therapy (e.g., IV fluid resuscitation, mechanical ventilation, more than 2 doses of epinephrine for a life-threatening reaction) at any time should be discussed with the PI and discontinued from active therapy.

For specific questions related to dosing escalation or continuation of the same dose that are not answered in the above protocol, the PI will be available for questions and decision-making.

If, at any point in the study, the subject complains of new onset vomiting, dysphagia, chronic abdominal pain, and/or difficulty swallowing for more than 2 weeks despite use of daily anti acids (<https://www.webmd.com/heartburn-gerd/qa/what-are-examples-of-antacids>), the subject will be given daily proton pump inhibitors (dosed per age and weight) <https://medlineplus.gov/ency/patientinstructions/000381.html> and if no relief occurs in 2 weeks, they will be referred to a gastroenterologist for assessment of possible gastroenterological disorders associated with food allergy (i.e., eosinophilic esophagitis). If at any point, side effects develop from the use of antacids or PPIs, the subject will be discontinued for the concomitant medication and referred to a GI specialist.

Any subject who discontinues build-up dosing due to repeated allergic reactions to the characterized food allergen will have his/her blood drawn for mechanistic studies within approximately 1 week of discontinuation of therapy.

6.4.3 Treatment for reactions during the Build-up and Maintenance Phase

Generally, for mild and moderate symptoms, the subject should receive antihistamines, and for more severe symptoms, the subjects should receive epinephrine, antihistamines, and then the other medications as indicated. Epinephrine can be used to treat any reaction (mild to severe) at the discretion of the investigator

If severe symptoms that do not meet the treatment stopping criteria occur at any time, decisions about participant continuation will be discussed with the NIAID Medical Officer.

Antihistamines

If a subject requires only antihistamines for treatment of allergic symptoms, the dose escalation can be continued. If symptoms during a build-up day require antihistamines in multiple doses or in combination with other medications (except epinephrine), there should be a dose reduction by 1-2 doses with the next dose given in SNP-CRU. If dose escalation fails or requires treatment after two more escalation attempts each spaced 2 to 4 weeks apart, the dose should be reduced to the last tolerated dose and continued long term without further escalation.

Epinephrine

Any reaction (in SNP-CTRU or at home) that requires two or more doses of epinephrine will require evaluation by study team before further OIT doses are administered. OIT dose will be reduced and administered under observation in CTRU. In the event the patient is unable to return to clinic, the patient should contact study clinician for further guidance.

SNP-CRU

If a single administration of epinephrine is required during in SNP-CRU escalation, the dose should be reduced by two doses, and the subject continued on that dose for four weeks. After 4 weeks at the reduced dose, an escalation attempt may be tried in SNP-CRU.

If a single administration of epinephrine is required a second consecutive time during this escalation attempt, the dose should be reduced by two doses, and the subject continues on that dose for 6-8 weeks. After 6-8 weeks at the reduced dose, an escalation attempt may be tried in SNP-CRU.

If a single administration of epinephrine is required a third consecutive time during this escalation attempt, the dose should be reduced by two doses and the subject continued on that dose as long-term maintenance without further escalation.

Home

If a single administration of epinephrine use occurs during dosing at home, this epinephrine use is not counted as one of the uses described above, unless severe anaphylaxis occurs at home. The subject should return to SNP-CRU for an observed dose prior to resuming any dosing at home. In the event the patient is unable to return to clinic, the patient should contact study clinician for further guidance.

6.5. Premature Discontinuation of Investigational Agent

Study therapy may be prematurely discontinued for any participant for any of the following reasons:

- Poor control or persistent activation of secondary atopic disease (e.g., AD, asthma)
- Started on beta-blockers, or other prohibited medications, with no alternative medications available per the prescribing physician
- Non-adherence with home OIT dosing protocol (excessive missed days; i.e., > 20 consecutive days) without consulting with study staff would be a safety issue warranting discontinuation
- The subject develops biopsy-documented eosinophilic esophagitis (EoE) with synchronous clinical symptoms or other eosinophilic gastrointestinal disease
- Study therapy may also be prematurely discontinued for any participant if the investigator believes that the study treatment is no longer in the best interest of the participant.

Study therapy may also be prematurely discontinued for any participant if the investigator believes that the study treatment is no longer in the best interest of the participant.

Follow-up of Subjects Who Discontinue Treatment Only

Subjects who prematurely discontinue treatment with OIT may remain in the study until the end of study visit at Week 58.

Subjects who initiate therapy (i.e., who do not fail the Initial dose day AND initiate home dosing) in this trial will not be replaced.

7. Other Medications

7.1. Concomitant Medications

7.1.1. Protocol-mandated

There are no protocol-mandated concomitant medications.

7.1.2. Other permitted concomitant medications

All subjects may continue their usual medications, including those taken for asthma, allergic rhinitis and atopic dermatitis, during the study. However, they must be able to discontinue antihistamines prior to the initial day of escalation, skin testing and all oral food challenges. Usual topical steroid use is permitted at the time of skin testing. Up-dosing will not occur within 3 days of systemic steroid use.

7.2. Prophylactic Medications

There will be no prophylactic medications required in this protocol.

7.3. Prohibited Medications

Participants will be removed from the trial if any of the following meds are started and cannot be safely stopped:

- Omalizumab (Xolair)
- Oral β -blockers

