11.2. Participant Stopping Rules and Withdrawal Criteria

Participants may be prematurely terminated from the study for the following reasons:

1. The participant elects to withdraw consent from all future study activities, including follow-up.
2. The participant is “lost to follow-up” (i.e., no further follow-up is possible because attempts to reestablish contact with the participant have failed).
3. The participant dies.
4. The Investigator no longer believes participation is in the best interest of the participant.
5. Individual safety stopping rules:

The participant experiences an allergic reaction to any IP (CoFAR Grade 4; see Table in section 12.3.1).

Table in section 12.3.1 (page 49)

- i. **CoFAR Grading Scale for Systemic Allergic Reactions Modified Version 2.0** Any subject deemed to have severe allergic reactions and who receives aggressive therapy (e.g., IV fluid resuscitation, mechanical ventilation, repeated doses of epinephrine for a life-threatening reaction) at any time should be discontinued from further therapy
- ii. Other circumstances including, but not limited to, the following:

- Severe adverse event, other than anaphylaxis, related to investigational product
- Pregnancy

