11.4. Follow-up after Early Study Withdrawal

Subjects who prematurely discontinue treatment with OIT may remain in the study until end of study visit at week 58 to monitor safety and efficacy parameters. These visits will include skin testing and/or a blood draw for mechanistic studies at the study time points.

If the subject refuses this follow-up, or begins and then elects to discontinue the follow-up, they will be asked to come in for a final study visit consisting of a physical assessment, skin test, blood draw, review of their Food Allergy Action Plan, and instructions to discontinue any OIT dosing and continue food allergen avoidance.

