Appendix 2: Participant Disposition

If pregnancy or if hypotensive event related to study drug occurs, participants will be terminated from the study

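### Sections 7.3 and 6.5, and Appendix 2 and 6.4.2, give the same event two dispositions (leave the study, or stop OIT only), so week-52 data and safety follow-up after such events are not defined

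*Combined protocol and SAP*

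**What the plan says.** All references are to the combined protocol and SAP.

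**Prohibited medication.** Section 7.3, on omalizumab and oral beta-blockers: "Participants will be removed from the trial if any of the following meds are started and cannot be safely stopped". Section 6.5 lists among the reasons for discontinuing study therapy: "Started on beta-blockers, or other prohibited medications, with no alternative medications available per the prescribing physician". The synopsis repeats that item. Section 6.5 then adds: "Subjects who prematurely discontinue treatment with OIT may remain in the study until the end of study visit at Week 58".

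**Hypotensive or Grade 4 reaction.** Appendix 2: "If pregnancy or if hypotensive event related to study drug occurs, participants will be terminated from the study". Section 11.2 opens with "Participants may be prematurely terminated from the study for the following reasons" and includes: "The participant experiences an allergic reaction to any IP (CoFAR Grade 4; see Table in section 12.3.1". Item i of that same list, on severe reactions given aggressive therapy, stops therapy and does not mention leaving the study. Section 6.4.2 names hypotension and says that such participants "should be discussed with the PI and discontinued from active therapy". Section 11.4: "Subjects who prematurely discontinue treatment with OIT may remain in the study until end of study visit at week 58", with skin testing and/or blood draws at the study time points.

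**Pregnancy.** Appendix 2 ends study participation, and 11.2 lists pregnancy as a ground for termination. Section 12.6 has the participant stop study medication and follows the pregnancy to its conclusion.

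**What the analysis needs.** Section 13.4.2 models change in CD28 from baseline to week 52 on an indicator of passing the week-52 food challenge (DBPCFC). Section 13.2.1 sets those who pass against everyone else, and 13.4.1 puts all enrolled participants in the ITT sample. Section 13 has no rule for a participant without a week-52 CD28 value or without a week-52 challenge. Section 12.4.1 stops adverse event collection 30 days after premature withdrawal from the study.

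**The concern.** Stopping treatment and leaving the study are different events for the data. A participant who stops OIT but stays can still give week-52 blood and report adverse events to week 58. A participant removed from the study cannot be relied on for either. Where two sections give different dispositions for one event and neither takes precedence, the available data depend on which section staff apply to that participant.

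This matters most for participants who stop before week 52 because of a Grade 4 or hypotensive reaction. Section 3.1 counts withdrawals for unacceptable side effects as treatment failures, and under 13.2.1 they fall among those who did not pass. Losing their week-52 CD28 therefore depends on the outcome that defines the primary contrast, and it affects the smaller group. They are also the participants for whom longer safety follow-up is most informative.

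**Working it through.** **1. Compare the rules event by event.**
- Prohibited medication: 7.3 is mandatory and ends trial participation. Section 6.5 ends therapy and allows follow-up to week 58. This is a direct conflict.
- Hypotension treated aggressively: Appendix 2 is mandatory and ends study participation. Section 6.4.2 and item i of 11.2 end therapy, and 11.4 allows follow-up to week 58. This is a conflict, though 6.5 does not list the event.
- Grade 4 reaction: 11.2 permits termination but does not require it. Its lead-in (study) and its item i (therapy) differ.
- Pregnancy: stopping medication and following the pregnancy can coexist with study exit. Week-52 and week-58 participation is unclear, but this is not a flat contradiction.

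**2. Size of the group at risk** (13.7: 72 participants).
- At 81% desensitized: 0.81 × 72 = 58.3, so 58 passers and 72 − 58 = 14 non-passers. One loss is 1/14 = 7.1%.
- At 85%: 0.85 × 72 = 61.2, so 61 passers and 11 non-passers. One loss is 1/11 = 9.1%.

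**3. Reproduce the plan's power.** Inputs from 13.7 and 13.4.2: difference 0.75, SD 0.90, correlation 0.5, two-sided 0.05. I assume that adjustment for baseline reduces the SD by √(1 − 0.5²).
- Residual SD = 0.90 × √0.75 = 0.779.
- Noncentrality = 0.75 / (0.779 × √(1/58 + 1/14)) = 3.23, with 72 − 3 = 69 df.
- Power = 89.0%, against 87% stated. The same method gives 82.5% for 61 versus 11 (stated 82%) and 81.1% for 50 versus 11 under 15% missing (stated 80%). This is close enough to use.

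**4. Remove non-passers only.** The number lost is an assumption, because the documents give none. The 58 passers are kept.

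| Non-passers lost | Left | Power |
|---|---|---|
| 0 | 14 | 89.0% |
| 1 | 13 | 87.1% |
| 2 | 12 | 84.9% |
| 3 | 11 | 82.2% |
| 4 | 10 | 79.1% |

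Starting from 50 versus 11, one further loss gives 78.0%. With no gain from the baseline correlation, one loss from 58 versus 14 takes power from 78.8% to 76.4%. Either way the step is 2 to 3 points.

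**5. Expected count.** Section 5.2 (medical literature) expects severe symptoms in under 1% of subjects. Since 1% of 72 is 0.72, this points to fewer than one participant.

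**6. Safety follow-up.** If a participant exits at week *s*, collection ends at *s* + 30/7 = *s* + 4.3 weeks under the removal wording, and at week 58 if the participant is retained. The difference is 53.7 − *s* weeks. Taking *s* = 20 as an illustration gives about 34 weeks, and *s* = 40 gives about 14.

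**The case against.** The case for treating this as minor is substantial, and most of it stands.

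- Section 6.5 lists neither hypotension, Grade 4 reactions nor pregnancy. Only prohibited medication overlaps with it directly.
- Starting a beta-blocker or becoming pregnant is not a measure of response to OIT. A reader might infer that all these exits strip the worst responders from the comparison. That reasoning applies only to reaction-driven exits.
- Section 11.2 says participants may be terminated, and 11.4 says they may remain. Two permissive rules can coexist. This does not help with 7.3 and Appendix 2, which are mandatory.
- A reader might infer that removal means no further samples. Section 11.4 is headed as follow-up after early study withdrawal and offers a final visit with blood, and 6.4.2 calls for mechanistic blood within about a week when build-up stops for repeated reactions. These help, but neither final-visit nor discontinuation blood is a week-52 value.
- The trial has one site, so practice would vary between participants, not between sites.
- Section 13.7 already allows for 15% or 20% missing CD28. That covers the number lost, not loss related to outcome.
- Sections 3.1 and 8.3 refer to Appendix 2 for disposition by tolerated dose, and the text available for this review holds one sentence of it. A diagram might add detail, but that sentence is explicit.
- Retention alone does not place a participant in the contrast. Section 11.4 lists no DBPCFC, and the definitions separate treatment failure from desensitization failure.

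**Conclusion.** The point holds in a limited form. Section 7.3 conflicts with 6.5 on prohibited medication, and Appendix 2 conflicts with 6.4.2 and item i of 11.2 on hypotensive reactions treated aggressively. Nothing ranks these rules. Section 11.2 is internally unclear on Grade 4 reactions, and pregnancy leaves later visits unsettled without being a contradiction.

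The documents do not support the stronger inference that the primary analysis is materially underpowered or already biased by these rules. The number of reaction-driven exits is not stated and is probably small, and one loss costs about 2 points of power (89.0% to 87.1%, assuming the baseline adjustment above). What remains is outcome-dependent loss from a group of about 14 (or 11), at 7% to 9% per participant, and adverse event collection cut to 30 days after exit. Both apply only if the removal wording is followed and the exit comes before week 52. That justifies a wording change. Which event should stop OIT or end participation is not judged here.

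**What to change.** The sponsor should reconcile the synopsis, 6.4.2, 6.5, 7.3, 11.2, 11.4, 12.6 and Appendix 2 so that each event has one stated disposition, using separate terms for the end of OIT dosing and the end of study participation. The clinical criteria, and the disposition each event receives, are for the sponsor to decide.

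Wherever the reconciled disposition is that OIT alone ends, the protocol should state:
- that adverse event collection continues, and that the scheduled week-52 and week-58 non-challenge assessments, including blood for CD28, are done unless consent is withdrawn and where the investigator judges them safe;
- how these participants are classed in the pass-versus-all-others contrast when no week-52 DBPCFC is done.

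The cost is protocol wording and a few more follow-up visits for participants off OIT, at time points already in the schedule of events.
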